2.1 STUDY OBJECTIVES

2.1.1 Primary Objectives

The primary objectives are to compare the safety, efficacy and tolerability of three MOD-4023 doses to that of a commercially available standard daily r-hGH formulation, in pre-pubertal children with growth failure due to insufficient secretion of endogenous growth hormone.

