5.1.2 Visit 1 – All Patients

This visit will take place in the medical center for all patients on the day of the first dose. The following procedures will be performed (prior to dosing for MOD-4023 cohorts):

1. Physical examination including height and weight;

¹ Central laboratory results will be used for eligibility confirmation.

OPKO Biologics	Protocol for Clinical Study CP-4-004	Page 49 of 133
Effective Date: Date of final electronic approval		

2. Vital signs (within one hour prior to dosing);
3. AEs, local tolerability;
4. Concomitant medications;
5. Parameters of glucose metabolism (fasting glucose, insulin, and HbA1C);
6. Other hormonal levels (TSH, free T4, free T3, cortisol);
7. Baseline antigenicity (anti MOD-4023 antibodies for cohort 1-3 patients) and anti hGH for Genotropin patients
8. Routine safety biochemistry and hematology;
9. Parameters of lipid metabolism (with Lp(a) lipoprotein);
10. IGF-I and IGFBP-3 serum levels, baseline MOD-4023 (cohorts 1-3) and Genotropin (cohort 4) levels;
11. Training for parents or legal guardians on drug administration.

Patients allocated to the MOD-4023 cohorts will be administered the first dose by the study staff in the morning hours, after completion of all of the above.

The following procedures will be performed after dosing (for MOD-4023 cohorts):

1. Vital signs: 30 min, 2 hours (± 20 min) and 4 hours (± 20 min) post dose;
2. Injection site reaction: 30 min and 4h (± 20 min) after injection.

Patients allocated to the Genotropin cohort will be administered the first dose at home in the evening hours.

5.1.3 PK/PD Visits (V2 - Week 2; V3 - Week 4; V4 -Week 6)

All patients randomized to receive one of the three MOD-4023 doses will start treatment for 2 weeks with the low MOD-4023 dose (0.25 mg protein/kg). Based on the patient's dose allocation, this will be followed by a dose increase to the next dose level every two weeks until the final allocated dose is reached (see [Table 5](#)).

Subsequent to the second dose administration of the targeted dose, limited (population based) PK and PD sampling will be taken (according to [Table 6](#) and [Table 7](#)).

Patients allocated to a MOD-4023 dose cohort (cohorts 1-3) will be randomized within the cohort into one of three blocks and undergo limited PK/PD sampling (4 samples per patient over a period of one week), according to [Table 6](#) below.

OPKO Biologics	Protocol for Clinical Study CP-4-004	Page 50 of 133

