Effective Date: Date of final electronic approval		

TABLE 6: MOD-4023 POPULATION PK AND PD SAMPLING SCHEME

Visit (V2, V3, V4)	a		b	c	d	e	f	g	
Time after dosing(h)/ Block number	0h	6h	12h	24h	48h	72h	96h	120h	168h
Block 1									
Block 2									
Block 3									

Patients allocated to the Genotropin dose cohort (cohort 4) will be randomized within the cohort into one of three blocks and undergo limited PK/PD sampling (4 samples per patient over a period of 24 hours), according to [Table 7](#) below.

TABLE 7: GENOTROPIN POPULATION PK AND PD SAMPLING SCHEME (VISIT 2)

Time after dosing(h)/ Block number	0h	1h	2h	4h	6h	12h	16h	20h	24h
Block 1									
Block 2									
Block 3									

This blood sampling schedule may require hospitalization for some of the patients due to convenience reasons.

During the first 6 weeks of the study, the visit schedule will be as follows (see scheme in [Appendix 1: Schedule of Assessments – Main Study](#)):

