Patients allocated to Cohort 4 will perform Visits 2 and 4. Cohort 4 patients will skip Visit 3 (week 4).

Patients allocated to the Genotropin cohort (cohort 4) will return to the medical center for visits 2 and 4 during the 2nd and 6th week of treatment. The following procedures will be performed (prior to dosing if dosing is done at the medical center):

1. Physical examination;
2. Vital signs;
3. AEs, local tolerability;
4. Concomitant medications;
5. Parameters of glucose metabolism - fasting glucose, insulin, and HbA1C (V4 only);
6. Routine safety biochemistry, hematology, and urinalysis parameters (week 6 only – visit 4);
7. IGF-I and IGFBP-3 serum levels;
8. Genotropin serum levels.

In addition, after the 8th Genotropin dose (at the beginning of week 2 of dosing) the patients allocated to the Genotropin cohort will undergo limited PK/PD sampling according to [Table 7](#) above. Patients allocated to the Genotropin dose cohort (cohort 4) will be randomized within the cohort into one of three blocks and undergo limited PK/PD sampling (4 samples per patient over a period of 24 hours), according to following scheme:

OPKO Biologics	Protocol for Clinical Study CP-4-004	Page 55 of 133
Effective Date: Date of final electronic approval		

Time after dosing(h)/ Block number	0h	1h	2h	4h	6h	12h	16h	20h	24h
Block 1									
Block 2									
Block 3									

5.1.4 Monthly Follow Up Visits: Visit 5 (wk10), Visit 6 (wk14), Visit 7 (wk18), Visit 8 (wk22) - All Patients

These visits will be performed on a monthly basis for all patients. For patients allocated to MOD-4023 dose cohorts, the visit will take place 4(-1) days after dosing. For patients allocated to Genotropin cohort, the visit will take place on any day during the dosing week.

The following assessments will be performed:

1. Physical examination and vital signs;
2. AEs, local tolerability, and concomitant medications;
3. Parameters of glucose metabolism: fasting glucose, insulin (every visit), HbA1c (only visit 6);
4. Other hormonal levels: TSH, free T4, free T3, cortisol (only visit 6);
5. Routine safety biochemistry, hematology, and urinalysis parameters;
6. Patient's height;
7. Patient's weight;
8. Parameters of lipid metabolism (with Lp(a) lipoprotein at visit 6);
9. PD: IGF-I and IGFBP-3 serum levels;
10. MOD-4023 (cohort 1-3) and Genotropin (cohort 4) serum levels;
11. Adjustment of dose to patient's weight (only visit 6).

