5.7.3 Local Injection Site Reactions

Assessment of local tolerability will be performed by examining the injection sites (by the Investigator if a reaction is present at the time of a visit) and on the basis of anamnestic data and records in the patient diary.

The abnormal injection site reaction is defined as:

- Injection site reaction which is observed at the time of visit and moderate to severe in intensity.
- Injection site reaction between the last and present visit, or remaining at the time of visit which require medical attention, or injection site reaction resulting from a previous injection, other than the last injection.
- Any other injection site reaction deemed abnormal to the investigator's judgment, other than those ordinarily observed in subcutaneous injections.

Observations will be recorded on appropriate eCRF pages. If an injection site reaction meets the criteria defined for an “abnormal result” it will be considered an AE.

- Pain and Tenderness: For patients in all Cohorts, injection site pain will be evaluated by the investigator or designated personnel if the injection is given at the medical center, and by the parent/legal guardian if the injection is given at home. The pain will be evaluated using the XXXXXXXXXX Pain Rating Scale ([Appendix 8](#)). In addition,

OPKO Biologics	Protocol for Clinical Study CP-4-004	Page 71 of 133
Effective Date: Date of final electronic approval		

each patient and parent/guardian will be queried during study visits regarding possible injection site pain.

- Site status: For patients in all Cohorts, injection site status will be evaluated by the Investigator, or designated using the Injection Site Assessment Visual Analogue Scale ([Appendix 8](#)) at each of the PK/PD sampling time points. In addition, each patient and parent/guardian will be queried during study visits regarding possible site reactions.

The Investigator's Local Assessment of Tolerability eCRF page will be designed to capture the following information.

- Description of the reaction;
- Location: left arm/right arm/left thigh/right thigh/left buttock/right buttock/left part of abdomen/right part of abdomen;
- Duration: Onset, end date;
- Intensity: grading according to the scales provided in appendices;
- Action taken: action(s) taken by patients, medical intervention or concomitant medication;
- Comments.

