Patient-reported local site reactions and diary records will be captured on the "Local Tolerability assessment" CRF page. Only data about reaction type (e.g. pain, erythema, etc.), frequency, and intensity will be captured.

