8.5 SAFETY EVALUATION

The assessment of safety will be based mainly on the frequency of AEs, frequency of anti-MOD-4023 antibody development and on the number of laboratory values that fall outside of laboratory normal ranges. Other safety data (e.g. vital signs, special tests, etc.) will be considered as appropriate.

AEs will be listed by treatment group and patient for the treatment phase. AEs will be summarized by presenting, for each treatment group, the number and percentage of patients having any AE, having an AE in each body system and having each individual AE. Any other

OPKO Biologics	Protocol for Clinical Study CP-4-004	Page 97 of 133
Effective Date: Date of final electronic approval		

information collected (e.g. severity or relatedness to study medication) will be listed as appropriate.

Summaries and analyses will be based on treatment-emergent adverse events (TEAE), which are defined as AEs occurring after the first administration of study medication (as recorded on the study discontinuation / end of study CRF) or AEs present before the first dose and ongoing after administration with increased severity. Other AEs (pre-treatment AEs) will only be listed.

If appropriate, laboratory and/or ECG data will be summarized by presenting shift tables using extended normal ranges (baseline to most extreme post-baseline value), by presenting summary statistics of raw data (means, medians, standard deviations, ranges) and change from baseline values and by the flagging of notable values in data listings.

Blood glucose, HbA1c, cortisol, thyroid panel tests and lipid panel tests (with special attention on LpA) will be evaluated using standard descriptive statistics, the number of patients who had values outside normal values, and by listing values considered clinically relevant by the investigator.

Data from other tests (e.g. blood pressure or vital signs) will be listed, notable values will be flagged, and any other information collected will be listed as appropriate. Summary statistics will be given where appropriate.

In addition the number and percentage of patients developing antibodies, including neutralizing antibodies, will be summarized by cohort.

Local tolerability will be summarized based on the investigator's assessments of pain, tenderness, erythema, warmth and swelling which will be done by a scale and predetermined schedule during intensive PK/PD sampling.

The safety analysis will be performed based upon the safety analysis subset.

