Return and accountability of study medication														X	X	X	
Return and review of patient diary														X	X	X	

¹ Dose adjustment will be made according to weight measured on three monthly bases.

² Heart rate, blood pressure, body temperature, respiratory rate.

³ Only for patients for which the insulin-stimulation test has not been used or glucagon test has shown peak cortisol level below 500 nmol/l. Will be done at any point during the study if there is suspicion of de novo hypoadrenalinism.

OPKO Biologics	Protocol for Clinical Study CP-4-004	Page 111 of 133
Effective Date: Date of final electronic approval		

⁴ Earlier if there are clinical signs of intracranial hypertension.

⁵ Vital signs: for all patients allocated to cohorts 1- 3 (MOD) - Pre-dose and at 30 mins, 2h (\pm 20 mins) and 4h (\pm 20mins); for patients in cohorts 4 (Genotropin) at any time during the visit.

⁶ Injection site reaction: 30 min and 4h (\pm 20 min) post dosing for MOD-4023 cohorts and at any time during the visit for patients in cohort 4 (Genotropin).

⁷ Insulin tolerance test, with cortisol response to hypoglycemia if insulin stimulation test is chosen / Arginine test / Clonidine test / Glucagon test (plus or without propranolol) / L-dopa plus propranolol. At least one of the two stimulation tests must be analyzed by the central lab.

⁸ with Lp(a) lipoprotein.

⁹ Last MOD-4023 dosing 4 (-1) days before V12.

¹⁰ Last Genotropin dosing 1 day before V12.

OPKO Biologics	Protocol for Clinical Study CP-4-004	Page 112 of 133
Effective Date: Date of final electronic approval		

MOD-4023 Dose Cohorts (Cohorts 1-3) PK/PD Sampling Scheme

Visit	a		b	c	d	e	f	g	
Time after dosing(h)/ Block number	0h	6h	12h	24h	48h	72h	96h	120h	168h
Block 1	3.5 ml			3.5 ml	3.5 ml		3.5 ml		
Block 2		3.5 ml			3.5 ml	3.5 ml		3.5 ml	
Block 3			3.5 ml	3.5 ml		3.5 ml			3.5 ml

Genotropin Dose Cohort (Cohort 4) PK/PD Sampling Scheme

Time after dosing(h)/ Block number	0h	1h	2h	4h	6h	12h	16h	20h	24h
Block 1	3.5 ml		3.5 ml	3.5 ml			3.5 ml		
Block 2		3.5 ml		3.5 ml	3.5 ml			3.5 ml	
Block 3			3.5 ml		3.5 ml	3.5 ml			3.5 ml

OPKO Biologics	Protocol for Clinical Study CP-4-004	Page 113 of 133
Effective Date: Date of final electronic approval		

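### The local tolerability summary named in section 8.5 rests on one PK/PD-sampled injection per child, scored at times that differ between MOD-4023 and Genotropin, and milder later reactions have no named summary

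*Protocol*

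**What the plan says.** Protocol section 2.1.1 makes tolerability part of the main question: "The primary objectives are to compare the safety, efficacy and tolerability of three MOD-4023 doses" with that of daily r-hGH. Section 2.2 lists local injection site assessment as a safety endpoint for all study periods.

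Section 8.5 names one summary of local tolerability. It uses the investigator's assessments, "which will be done by a scale and predetermined schedule during intensive PK/PD sampling".

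The sampling window is defined elsewhere:

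- For MOD-4023, section 5.1.3 gives "4 samples per patient over a period of one week", after the 2nd, 4th or 6th weekly dose for Cohorts 1, 2 and 3.
- For Genotropin, the same section gives "4 samples per patient over a period of 24 hours". Section 5.1.3.4 places this "after the 8th Genotropin dose (at the beginning of week 2 of dosing").

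Two passages set the timing of site checks. Section 5.7.3 asks for site status in all cohorts "at each of the PK/PD sampling time points". Footnote 6 of Appendix 1 adds checks at 30 minutes and 4 hours "post dosing for MOD-4023 cohorts and at any time during the visit for patients in cohort 4 (Genotropin").

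Local tolerability is also collected for the rest of the year: at the monthly visits (5.1.4), week 26 (5.1.6), and months 9 and 12 (5.1.7). Diary and patient-reported reactions go on the Local Tolerability assessment CRF page, for which section 5.7.3 states: "Only data about reaction type (e.g. pain, erythema, etc.), frequency, and intensity will be captured".

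**The concern.** Genotropin is given only in the Main Study (6.1.4), so those 12 months hold the only randomised comparison of tolerability with daily treatment. The one local tolerability summary described for them uses a small early part of treatment, and the arms are looked at on different clocks within it. A difference between cohorts in those scores would mix drug, time since injection and number of earlier injections. Mild reactions that persist or begin after the sampling window, in any arm, would have no described place in the local tolerability results, although the sites and families have recorded them.

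**Working it through.** The plan states no figure on this point, so there is none to reproduce. The check is a count of coverage and a comparison of schedules.

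**Coverage of treatment.** One injection per child falls in the sampling window.

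- MOD-4023: 1/52 = 1.9% of weekly injections in 12 months.
- Genotropin: 1/365 = 0.27% of daily injections.

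**Scheduled times by block, in hours after dosing.** Sampling points come from the tables at the end of Appendix 1. The 0.5 h and 4 h checks for MOD-4023 come from footnote 6 and sections 5.1.3.1 to 5.1.3.3.

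| Block | MOD-4023 sampling points | MOD-4023 timed checks | Genotropin sampling points |
|---|---|---|---|
| 1 | 0, 24, 48, 96 | 0.5, 4 | 0, 2, 4, 16 |
| 2 | 6, 48, 72, 120 | 0.5, 4 | 1, 4, 6, 20 |
| 3 | 12, 24, 72, 168 | 0.5, 4 | 2, 6, 12, 24 |

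Genotropin children also have a site check at no fixed time during the visit.

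**What the schedules imply.**

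- Sampling points pooled over blocks: the MOD-4023 median is 48 h, with 7 of 12 later than 24 h. The Genotropin median is (4 + 6)/2 = 5 h, with 0 of 12 later than 24 h.
- Adding the two timed checks per block gives 18 MOD-4023 times. Their median is (12 + 24)/2 = 18 h, and 7 of 18 are later than 24 h.
- Scheduled post-dose looks per child, leaving out the 0 h point and the untimed check: 5, 6 and 6 for MOD-4023 Blocks 1 to 3, against 3, 4 and 4 for Genotropin.
- Up to and including 24 h, the numbers of looks are close: 3, 3 and 4 for MOD-4023, and 3, 4 and 4 for Genotropin. The real differences are the fixed 30-minute check and everything after 24 h, both in the MOD-4023 arms only.
- Injections received before the scored one: 1, 3 and 5 for Cohorts 1, 2 and 3, and 7 for Genotropin.

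**What happens to later reactions.** Under section 5.7.3 a reaction is abnormal, and therefore an AE, in any of these cases: it is moderate to severe at a visit; it needed medical attention; it comes from an injection before the last one; or the investigator judges it abnormal. Section 8.5 summarises AEs by treatment group over the treatment phase. A later reaction that meets none of these conditions is collected, but 8.5 names no summary for it.

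**The case against.** The strongest reply has four parts.

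**Section 8.5 does not exclude other data.** It describes one summary and does not say it is the sole one. Section 8.1 says data for all safety endpoints will be listed and tabulated, and it leaves methods to a SAP. The SAP supplied covers the extension periods only, so the planned Main Study tables cannot be seen. This stands. A reader might infer that Main Study tolerability will be summarised solely from the PK/PD window; the documents do not establish that. But the general sentence in 8.1 fixes no source, time window or worst-grade rule, and the specific sentence in 8.5 is the only one that does.

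**Later reactions that matter become AEs.** This also stands. It would be wrong to infer that late reactions are lost: abnormal ones enter the by-arm AE tables, and section 4.6 treats lipoatrophy as an AE. What is left is the milder reactions. The AE route is not quite even between arms either. A reaction from an injection before the last qualifies after about a day on daily dosing, but only after about a week on weekly dosing.

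**The direction of bias is unknown.** A reader might infer that brief redness or pain is caught at 30 minutes on MOD-4023 but has gone by the time a Genotropin child is seen. The schedules do not support that. Section 5.7.3 with Appendix 1 has every Genotropin child scored at 1 or 2 hours after a dose, and Blocks 1 and 2 again at 4 hours. The untimed visit check adds to these scores and does not replace them.

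**The stakes are modest.** The plan calls all evaluations purely exploratory, and 8.5 rests safety mainly on AEs, antibodies and laboratory values. Section 1.4.1 shows that the 12-month results were already known when this version was written. That limits the remedy to supplementary descriptive tables.

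**Conclusion.** The point holds in a limited form. The local tolerability summary named in 8.5 draws on about 2% of MOD-4023 injections and 0.3% of Genotropin injections. Its timing differs by arm, so it is not a like-for-like comparison with Genotropin. Later reactions below the abnormal definition have no summary named there.

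The coverage figures assume 12 months of dosing as scheduled and one scored injection per child. The size and direction of any distortion cannot be determined. The documents give no reaction rates, and any per-injection risk put in to produce a number would be a bare assumption, as would independence between injections in the same child. The conclusion is that a stated analysis leaves out relevant data already collected for a component of the primary objective; it is not that the result is known to be biased.

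**What to change.** In section 8.5, or in the Main Study analysis as a supplement declared as such, add a by-cohort summary over the full 12 months. Use the local tolerability assessments from all visits and the diary-based CRF page. Report the number and percentage of children with any reaction by type, and the worst grade per child. Section 9.3 of the OLE SAP already uses maximum severity per patient for each 12-month period and can serve as the model. Its rule that missing scores count as the worst grade should be reconsidered first: read literally, one missing score in a year would put that child in the top category.

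Show the PK/PD-period scores in a separate table, with the schedules of the two arms stated in a footnote.

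Three practical limits:

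- Keep visit and diary data in separate columns. After week 6 most MOD-4023 visits fall 3 to 4 days after a dose, while Genotropin children may come on any day of daily dosing, so visit findings keep part of the timing problem.
- Do not plan measures that need dated diary entries, such as days with pain. The CRF page holds type, frequency and intensity only.
- List the reaction types. Section 8.5 names tenderness and warmth, which have no scale in Appendix 8, and omits bruising and itching, which do.

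The cost is a few descriptive tables from data already collected. The downsides are that diary reports are less standardised than clinic scores, and that the daily arm has about seven times as many injections at risk (365/52 = 7.0). Scheduled injections per cohort should therefore be printed beside the counts.

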8.6 PK/PD EVALUATION

PK/PD parameters will be calculated utilizing a population PK modeling approach, based on limited sampling in each patient.

The proposed analysis strategy will include the following steps:

1. Estimate the Population PK/PD means and variances using the Population PK/PD analysis.
2. Perform an Empirical Bayesian estimation to retrieve the individual PK/PD model Parameters.
3. Use these individual PK/PD estimates to generate individual concentration time profile using rich sampling to cover the entire desired time range for Non compartmental Analysis calculation.
4. Perform Non compartmental Analysis for estimation of AUC and Cmax.

OPKO Biologics	Protocol for Clinical Study CP-4-004	Page 98 of 133
Effective Date: Date of final electronic approval		

9. Ethics

9.1 ETHICS AND GOOD CLINICAL PRACTICE (GCP)

This study must be carried out in compliance with the protocol and the principles of Good Clinical Practice, as described in Sponsor/CRO standard operating procedures and:

1. ICH Harmonized Tripartite Guidelines for Good Clinical Practice 1996. Directive 91/507/EEC, The Rules Governing Medicinal Products in the European Community.
2. US 21 Code of Federal Regulations dealing with clinical studies (including parts 50 and 56 concerning informed consent and IRB regulations).
3. Declaration of Helsinki and amendments, concerning medical research in humans (Recommendations Guiding Physicians in Biomedical Research Involving Human Patients).

The investigator agrees when signing the protocol to adhere to the instructions and procedures described in it and thereby to adhere to the principles of ICH-Good Clinical Practice that it conforms to.

